Aim 1: Develop and iteratively refine BE-informed messages based on Veterans' perceptions, and incorporate them into enhanced appointment reminders.

Hypothesis: Perceptions of messages will be consistent with our conceptual framework and not associated with emotional harms.

Aim 2: Determine the effect of four versions of enhanced appointment reminders on measures relevant to treatment access, compared with usual reminders.

Hypotheses: 1. Each intervention group will have a lower no-show rate, as compared with usual care. 2. Each intervention group will have a higher advanced cancellation rate, as compared with usual care. Exploratory

Hypothesis: Wait time will be shorter in intervention groups than with usual care.

Aim 3: Evaluate differences in treatment effect associated with four versions of enhanced appointment reminders.

Hypothesis: Effect size of nudges will vary by intervention arm such that some types of nudges will have a larger proportional effect than others.

Aim 4: Characterize potential barriers and facilitators to widespread implementation of enhanced appointment reminder messages. We will conduct semi-structured interviews with key informants (10 Veterans locally and 30 VHA staff nationally). Interview guides will be informed by selected domains and constructs from the Consolidated Framework for Implementation Research.

SCIENTIFIC RATIONALE AND SIGNIFICANCE

BACKGROUND

Why are no-shows a critical health services issue now?

[figure not shown]
Providing and maintaining patient access to care has been declared by leadership as the Veterans Health Administration's (VHA) highest priority. Deficits in access have been shown to contribute to decreased patient satisfaction³⁷, higher mortality rates³⁸ and diminished quality of care³⁹. Amidst an environment of limited access and long wait times, VHA is simultaneously struggling with "no-shows."

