4. **Intervention feasibility:** We have conducted several tests to ensure smooth implementation of our proposed intervention. First, we have verified that patients have a very high probability of actually receiving pre-appointment letters or postcards. To evaluate this, [name] used administrative data to construct a sample of 1,110 VAPORHCS patients who had had an in-person primary care visit and positive depression screen in the last year. Of these patients, postal

addresses were correct for 95.6% based on phone and postal verification efforts. Second, we have confirmed that the vast majority of appointments are scheduled at least two weeks in advance, which is a timeframe used to determine whether to mail a reminder letter or postcard. To determine this, we extracted data comparing scheduled appointment “create date” and appointment date. Results from the VSSC pending appointment report showed that in July 2016, 92.8% of all VHA scheduled appointments nationally in mental health were created at least two weeks in advance (94.7% in primary care), with similarly high rates at VAPORHCS.

5. **Pilot effectiveness study:** We conducted a pilot effectiveness study of a version of the most basic proposed intervention. Reminder templates were changed on July 1, 2016 in randomly selected mental health clinics across VAPORHCS, and no-show rates were compared between intervention and control clinics in the pre-(April-June 2016) and post-intervention (July-Sept. 2016) periods. Difference-in-difference results showed an absolute decrease of 0.6% in no-shows, and 3.8% increase in appointment attendance in association with the intervention. This suggests that in three months in just a handful of clinics, over 100 no-shows were averted by making a one-time change to pre-appointment reminder templates. Assuming this same effect size and application to all mental health and primary care clinics in VAPORHCS, we estimate this basic intervention alone could avoid over 1,500 no-shows [.006*(102,060 mental health + 157,587 primary care appointments/year)].

Research Design and Methods

A. Design Overview:

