B. Data Source: Aims 1, 2, 3: All research material will be derived from existing records. VHA Corporate Data Warehouse (CDW) and VHA Support Service Center (VSSC) databases will be used to identify the main study sample and provide descriptive characteristics of the scheduled appointments and patients in our sample. VHA Survey of Healthcare Experiences of Patients (SHEP) data will be used to assess appointment wait time. Permissions will be obtained and data use agreements completed as appropriate to access data from CDW, VSSC, and SHEP. CDW data will be accessed via VA Informatics and Computing Infrastructure (VINCI) and will be saved locally. The research team has extensive experience obtaining permissions for, and working with, these data sources.

We will obtain data from these databases for up to two years preceding the study start date and two years following the study completion date. Variables extracted from these databases will include patient demographics (age, sex, race/ethnicity, service connection status, and rurality), patient diagnoses (proportion with common chronic conditions such as depression, PTSD, diabetes, and hypertension), appointment features (provider, location, specialty, clinic type, new vs. follow-up, date, outcome [i.e., completed, canceled, or no-show]).

Aim 4: Research materials will include audio files, transcripts, and cards/notes from qualitative interviews with patients. These materials will be obtained specifically for this research project.

C. Study Population:

Sample and Recruitment: This project has two primary study populations involved in the 4 Specific Aims:

1. Patients treated at VAPORHCS with at least 1 scheduled individual outpatient appointment in a primary care or mental health clinic during the 12-month intervention period (Aims 1, 2, and 3).
2. VHA staff located throughout VHA nationally (Aim 4).

We expect our study sites to yield patients with characteristics (except for race) very similar to elsewhere in VHA. Specifically, CDW data from the 12 months ending June 2016 indicate that our no-show rates vary from national figures by just 0.1% in mental

health and 1.5% in primary care (<0.5 standard deviation of variation). Similarly, there is <1% difference in proportion of Veterans with service disability, PTSD diagnosis, or male gender between local and national figures; mean age differs by just 1.6 years. Proportion of racial minorities (including unknown/declined) is 21% locally vs. 28% nationally.

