- Eligibility Criteria for Subjects: 1) patient with at least 1 ambulatory appointment scheduled at least two weeks before the appointment date during the study period; 2) appointment is in either primary care (limited to stop code 323) or mental health (limited to individual stop codes used by VSSC and tracked nationally: 502, 534, 513, and 540); and 3) 1 of the above eight VAPORHCS locations.
 - Exclusion Criteria for Veteran Subjects: 1) patients with hearing problems; 2) lack of regular access to a telephone
- Recruitment of Subjects: First, we will use CDW to identify all patients meeting the above eligibility criteria. Patients will be stratified along several criteria to promote purposive sampling based on: number of scheduled appointments in the prior 12 months (both primary care and mental health), number of scheduled appointments attended vs. no-showed in the prior 12 months, new vs. established patient, service era, and gender. Second, we will mail opt-out study invitations in batches of 50 letters. Third, we will conduct a phone call to determine Veteran interest in an in-person interview, as well as capacity to give informed consent. Fourth, during an in-person study visit, we will consent and enroll participants who indicated interest and have apparent capacity to give consent. We will enroll between 18-36 participants for the Aim 1 interviews and design sessions.

Aim 2 and Aim 3

- Eligibility Criteria for Subjects: 1) patient with at least 1 ambulatory appointment scheduled at least two weeks before the appointment date during the study period; 2) appointment is in either primary care (limited to stop codes 179, 322, 323, 324, 338, 690, 692, or 693) or mental health (limited to individual stop codes used by VSSC and tracked nationally: 502, 513, 527, 528, 542, 545, 534, and 540); and 3) 1 of the above eight VAPORHCS locations.
 - Exclusion Criteria for Veteran Subjects: 1) patients with hearing problems; 2) lack of regular access to a telephone

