Our primary outcome will be no-show rate, or the proportion of total appointments that are classified as a no-show, relative to the total number of appointments scheduled. The numerator (“no-shows”) consists of appointments marked as a no-show and appointments canceled by the patient or clinic after the appointment time. The denominator (“total appointments”) consists of no-shows and completed appointments. No-show rates will be measured at the provider-level.

Table 3. Trial Outcomes (Aims 2 & 3)

Outcome	Measure	Data Source
Primary	No-show rate	CDW
Secondary	Cancellation rate	CDW
	Advance cancellation rate	CDW
	Patient-initiated cancellation rate	CDW
Exploratory	Raw wait time	CDW
	Clinically indicated wait time	CDW
	Waiting room time	SHEP
	New mental health appointment wait time	CDW

Our secondary outcome will be cancellation rate, defined as the proportion of scheduled appointments that are marked as canceled. In addition to overall cancellation rate, we will also determine the rate amongst the subset of cancellations that are advance cancellations and patient-initiated cancellations. Advance cancellations, defined here as at least five days before appointment, provide a metric with a reasonable window of time (informed by preliminary data provided by our schedulers) that allows the opportunity to fill a cancelled slot with another waiting Veteran. Patient-initiated cancellations provide a more specific indication of intervention effects on cancellation behavior. Cancellation rates will be measured at the provider-level.

Finally, as exploratory outcomes, we will calculate wait time and number of unique patients seen per day. The latter is simply the number of daily completed encounters, adjusting for patients who have multiple encounters in the same day. For wait time, we will use multiple validated metrics:

- Raw wait time is defined as the length of time in days between the date an appointment was created and the date the appointment was completed⁷⁴. If an appointment is cancelled or a no-show, the wait time will be calculated based on the next appointment that is scheduled and completed in the same clinic stop code.

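### The two-week booking criterion is the only entry rule for the wait-time outcomes, and it can remove some of the short waits that the exploratory hypothesis predicts

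*Combined protocol and SAP*

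**What the plan says.** - **Entry criteria (Section D, Aim 2 and Aim 3).** The first criterion is worded for the patient: "patient with at least 1 ambulatory appointment scheduled at least two weeks before the appointment date during the study period". The second is worded for the appointment: "appointment is in either primary care (limited to stop codes 179, 322, 323, 324, 338, 690, 692, or 693", followed by a list of mental health codes.
- **Population (Section C).** The same patients are described as those "with at least 1 scheduled individual outpatient appointment in a primary care or mental health clinic during the 12-month intervention period", with no lead-time condition.
- **Reason for two weeks (Preliminary Studies, item 4).** It is a period "which is a timeframe used to determine whether to mail a reminder letter or postcard". A national pending-appointment report for July 2016 is cited: "92.8% of all VHA scheduled appointments nationally in mental health were created at least two weeks in advance (94.7% in primary care".
- **Wait-time hypothesis (Aim 2, exploratory).** "Wait time will be shorter in intervention groups than with usual care".
- **Raw wait (Section I).** "the length of time in days between the date an appointment was created and the date the appointment was completed". After a cancellation or no-show, the next completed visit in the same stop code is used. Clinically indicated wait starts from a date set by the provider, and new mental health wait runs from consult creation to consult completion.
- **Route to better access (Section I).** A cancellation at least five days ahead "allows the opportunity to fill a cancelled slot with another waiting Veteran".
- **Analysis (Section J).** The Cox model for wait time carries no lead-time limit and names no analysis set of its own.

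**The concern.** The two-week condition makes sense where a letter must have been mailed for the outcome to respond. Wait time is different. Raw wait is counted from the day of booking, so a minimum booking lead time selects on something very close to the outcome itself. That lead time arises after providers are randomised, and it is what the letters are hypothesised to shorten. Selection could therefore differ by arm: a provider whose freed slots are filled quickly would lose more short-wait Veterans or visits from the comparison than a provider whose slots are not.

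A slot released 5 to 13 days ahead can only be refilled by a booking made less than 14 days ahead. Such refills are one of the routes by which the plan expects access to improve. Section H says that letters go out at scheduling, so the raw wait of a visit kept as booked is already set when its letter is sent. Any effect on wait must come through refills, rebooked visits or a shorter queue. Losing part of the refills pulls the comparison toward no difference. The exploratory count of unique patients seen per day would lose the same visits if built on the filtered sample.

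**Working it through.** The plan gives no sample size or power for wait time, so there is no design figure to reproduce. The 92.8% and 94.7% shares come from a report whose counts are not given and are taken as stated.

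**Inputs from the documents**

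| Input | Value | Source |
|---|---|---|
| Booked 14 or more days ahead (national) | 92.8% mental health, 94.7% primary care | Preliminary Studies, item 4 |
| Appointments per 12 months | 102,060 and 157,587 | Section D |
| Unique Veterans | about 64,000 | Section D |
| Mean lead time, study system | 22–33 days | Section H |
| Arms | 5, equal allocation | Section G |
| Assumed difference in no-show and cancellation rates | 1.9% and 2.7% | Section K |

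**1. Per-patient reading (as worded).** Veterans whose every appointment was booked under 14 days ahead are lost; short-notice visits of all other Veterans stay in. The documents give no count. The average is 259,647 / 64,000 = 4.1 appointments per Veteran, so the group may be small. It would include a new mental health patient seen only in a freed slot.

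**2. Per-appointment reading: volume lost** (assuming that the national shares hold locally)
- Mental health: 100 − 92.8 = 7.2%; 0.072 × 102,060 = 7,348 a year, or 7,348 / 5 = 1,470 per arm.
- Primary care: 100 − 94.7 = 5.3%; 0.053 × 157,587 = 8,352 a year, or 1,670 per arm.
- Together: 15,700 / 259,647 = 6.0%.

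**3. Per-appointment reading: truncation of raw wait.** Assume gamma-distributed lead times with the stated mean and the stated share below 14 days. The mean among bookings of 14 days or more is then:
- overall mean 22 days: 22.8 (7.2% below 14 days) or 22.5 (5.3% below);
- overall mean 33 days: 34.7 (7.2%) or 34.2 (5.3%).

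**4. Per-appointment reading: which freed slots could still be refilled.** Assume cancellations are spread evenly from scheduling to five days before the visit. The share falling 14 or more days ahead is (m − 14)/(m − 5), where m is the mean lead time:
- m = 22: 8/17 = 47%, leaving 53% at 5–13 days;
- m = 33: 19/28 = 68%, leaving 32% at 5–13 days.

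**5. Per-appointment reading: size of the direct effect that could be hidden.** Suppose extra slots, a fraction x of all appointments, are refilled at about 9 days' notice (assumption). The mean raw wait falls by x(m − 9)/(1 + x):
- all of a 2.7% rise refilled (x = 0.027): 0.027 × 13 / 1.027 = 0.34 days (m = 22); 0.027 × 24 / 1.027 = 0.63 days (m = 33);
- a quarter refilled (x = 0.00675): 0.09 and 0.16 days.

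**6. Sensitivity of the lost share.** A report of pending appointments tends to under-count short-notice bookings, because they are pending for less time. An exponential lead time (assumption) with mean 22 or 33 days would put 1 − exp(−14/22) = 47% or 1 − exp(−14/33) = 35% below 14 days. The 6.0% may therefore be too low, and the local share should be obtained.

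**The case against.** The strongest reply is that the criterion selects patients. A Veteran who qualifies through one early booking is in, and nothing in the plan removes that Veteran's short-notice visits. The appointment totals in Section D, the power section, the no-show denominator and the Cox model likewise carry no lead-time filter. Clinically indicated wait, consult-based wait and waiting-room time do not start at appointment creation, so they are not cut off at 14 days. Wait time is exploratory. The Section C wording may simply be a summary of the fuller criteria in Section D.

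Most of this stands. A reader might infer that all refilled slots are excluded, that the wait-time effect would show as zero, or that the hypothesis cannot be answered. The documents do not support any of these. Refills at 14 or more days' notice survive even a per-appointment filter, as do the next-appointment provision for raw wait and any general shortening of a provider's queue. The 2.7% is an assumed rate difference, not a forecast of refilled slots, so the upper figures in step 5 are ceilings.

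Two things are not answered. Veterans seen only at short notice fall outside the study even on the literal reading, and that affects the consult-based and clinically indicated measures through entry to the sample. And because the second criterion has to work appointment by appointment, a programmer could reasonably apply the whole list that way.

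**Conclusion.** The concern holds in limited form. The only entry rule for wait time selects on a post-randomisation quantity closely tied to the outcome, and either reading can bias the comparison toward no difference.

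- **Per patient:** the loss is confined to Veterans seen only at short notice. It cannot be counted from the documents and may be small.
- **Per appointment:** about 7.2% of mental health and 5.3% of primary care appointments are lost, and raw wait is truncated at 14 days for visits kept as booked. A direct effect of 0.34–0.63 days could be hidden if every extra slot were refilled at about 9 days' notice, or 0.09–0.16 days if a quarter were.

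These sizes rest on national shares applied locally and on assumed lead-time, cancellation and refill patterns. The no-show and cancellation analyses are not affected. The wait-time hypothesis is weakened, not made unanswerable, but access is the trial's stated rationale, and a null wait-time result would be hard to interpret while the entry rule stands.

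**What to change.** In Section D, limit the two-week condition to the no-show and cancellation outcomes. In Sections I and J, state that raw wait, clinically indicated wait, new mental health wait and unique patients per day use all appointments or consults in the listed stop codes with a randomised provider, whatever the lead time, analysed by that provider's arm. Align the population statement in Section C with Section D, and report the local share of appointments booked under 14 days ahead.

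The cost is a few sentences and a wider filter on the same data warehouse extract. The 64,000-Veteran estimate already rests on all scheduled appointments, so the cap of 70,400 records should hold. The downside is small: the wait-time sample will differ from the no-show sample and will include visits for which no letter was mailed. The report should say so.

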By examining different types of nudges in different intervention arms, this project will help advance scientific understanding of the mechanisms behind behavior change related to appointment attendance. If successful, it would also lay the groundwork for a subsequent study where we would have the resources to conduct full factorial testing, identify optimal combinations of messages/nudges, and determine whether synergistic effects can be achieved by combining messages. **Table 2** contains a more detailed description of what kinds of messages fall into each of the four categories of nudges. For most of the four concepts, multiple draft messages are presented.

Table 2: Messages included in the appointment reminder based on the related concept

Concept	Message
Caring	We're here for you.
Consequences for Others	Call now so we can help another Veteran in need.
Consequences for Self	Attending appointments lowers your chances of being hospitalized.
Consequences for Self	If you miss your appointment, you may have to wait a while to be seen.
Social Norms	Most Veterans make a point to attend their VA appointments. If they can't make their appointments, most Veterans also make an effort to let us know.
Behavioral Instructions	Need to change or cancel your appointment? Take these 2 simple steps today: 1) Call the clinic at [contact]. 2) Give your name, last 4, and appointment information. It's fine to leave a message.

Intervention 1 (Social Norms + Behavioral Instructions): A letter with two types of nudges. One points out the common behavior of attending appointments. And one provides clear, specific instructions for making appointment changes. The appointment reminder also includes usual care (basic appointment information on date, location, and phone number(s) for scheduling changes).

Research has shown that social norms messages have a positive impact on behavioral action, however it is not clear how effective it is in comparison to messages framed around consequences. Additionally, we did not use the caring message in this intervention arm to allow for comparison of whether the caring message on its own has a positive impact.

Intervention 2 (Caring + Consequences for Others + Behavioral Instructions): A letter with three types of nudges. One suggests that the institution cares about the patient. One highlights a potential negative consequence for others if the patient no-shows. And one provides clear, specific instructions for making appointment changes.

The appointment reminder also includes usual care (basic appointment information on date, location, and phone number(s) for scheduling changes).

During the development of the conceptual messages the gain framed consequences for others message and the caring message both received favorable responses, and participants often put these messages together. These messages emphasize a personal connection between the recipient of the letter, the clinic, and other patients at the clinic. This positive message and personal connection calls upon a sense of social responsibility, which we anticipate will have a positive impact on no-show rates.

Intervention 3 (Caring + Consequences for Self + Behavioral Instructions): A letter with three types of nudges. One suggests that the institution cares about the patients. One highlights potential negative consequences for the patient if s/he no-shows. And one provides clear, specific instructions for making appointment changes. The appointment reminder also includes usual care (basic appointment information on date, location, and phone number(s) for scheduling changes).

On their own, each consequences-for-self message had mixed reactions. By including both messages we hope that if one concept does not appeal to a participant, that the second will. By including the caring message, we are conveying the idea that the reminder of the consequences if they no-show is coming from a place of caring for the recipient of the letter, and thus whether framed as a personal gain or loss the recipient may be more open to hearing the consequences-for-self messages and be gently nudged to action.

Intervention 4 (Caring + Consequences for Others + Consequences for Self + Social Norms + Behavioral Instructions): A letter with all four types of nudges combined. One suggests that the institution cares about the patients. One highlights a potential negative consequence for others if the patient no-shows. One highlights potential negative consequences for the patient if s/he no-shows. One points out the common behavior of attending appointments. And one provides clear, specific instructions for making appointment changes. The appointment reminder also includes usual care (basic appointment information on date, location, and phone number(s) for scheduling changes).

While we anticipate that each intervention arm will have an impact on No-Show rates, it is not clear which messaging combination will have the greatest impact. While we combine some messages, we also anticipate that combining more messages will not have an additive effect. Instead, too many messages may dilute the effectiveness of all the messages. To test this, we developed this intervention arm to include every

message, to determine if behavioral nudges are best used in shorter and smaller combinations.

H. Procedure: Because VHA appointments are managed in the Veterans Health Information Systems and Technology Architecture (VistA) and related data systems, letters and postcards will be designed and formatted within the constraints of VistA and related system requirements. The research team will work with and support clinical application coordinators in mental health and primary care to modify, audit, and maintain letter template changes. Our research team is experienced with staffing resources and procedures necessary in preparing large and customized patient mailings⁸⁵. Because letter templates are unique to each provider and his/her associated clinic(s), the research team will take advantage of this specificity when tailoring messages. Intervention content will be applied to pre-appointment reminder letters and/or postcards, which in VAPORHCS are mailed at the time of scheduling. (Our preliminary data shows that, as of July 2016, in VAPORHCS, appointments are scheduled, on average, 22-33 days before the appointment in primary care and mental health.) In addition, intervention content will also be adapted to no-show letters and/or postcards, which are sent after a no-show, to help reduce risk of repeated no-shows.

I. Measures:

Outcomes for Aim 2
(Determine the effect of four versions of enhanced appointment reminders on measures relevant to treatment access, compared with usual reminders) **and Aim 3** (Evaluate differences in treatment effect associated with four versions of enhanced appointment reminders): **Table 3** summarizes the outcomes used in these Aims.

Our primary outcome will be no-show rate, or the proportion of total appointments that are classified as a no-show, relative to the total number of appointments scheduled. The numerator (“no-shows”) consists of appointments marked as a no-show and appointments canceled by the patient or clinic after the appointment time. The denominator (“total appointments”) consists of no-shows and completed appointments. No-show rates will be measured at the provider-level.

Table 3. Trial Outcomes (Aims 2 & 3)

Outcome	Measure	Data Source
Primary	No-show rate	CDW
Secondary	Cancellation rate	CDW
	Advance cancellation rate	CDW
	Patient-initiated cancellation rate	CDW
Exploratory	Raw wait time	CDW
	Clinically indicated wait time	CDW
	Waiting room time	SHEP
	New mental health appointment wait time	CDW

Our secondary outcome will be cancellation rate, defined as the proportion of scheduled appointments that are marked as canceled. In addition to overall cancellation rate, we will also determine the rate amongst the subset of cancellations that are advance cancellations and patient-initiated cancellations. Advance cancellations, defined here as at least five days before appointment, provide a metric with a reasonable window of time (informed by preliminary data provided by our schedulers) that allows the opportunity to fill a cancelled slot with another waiting Veteran. Patient-initiated cancellations provide a more specific indication of intervention effects on cancellation behavior. Cancellation rates will be measured at the provider-level.

Finally, as exploratory outcomes, we will calculate wait time and number of unique patients seen per day. The latter is simply the number of daily completed encounters, adjusting for patients who have multiple encounters in the same day. For wait time, we will use multiple validated metrics:

- Raw wait time is defined as the length of time in days between the date an appointment was created and the date the appointment was completed⁷⁴. If an appointment is cancelled or a no-show, the wait time will be calculated based on the next appointment that is scheduled and completed in the same clinic stop code.
- Clinically indicated wait time accounts for the “return to clinic” date assigned by the patient’s provider. In this metric for established patients, wait time is defined as the length of time in days between the provider-entered clinically indicated date and the date of the appointment. This is to account for the fact that appointment create date as the start date for measuring wait times may not reflect patient or provider preferences of when the patient should be seen. Limitations in VHA scheduling software have prevented systematic capture of these data until summer of 2017 when a technological fix was implemented. Co-I [name] will be examining this metric in the spring of 2018 using a VHA national dataset, and we will include this measure if validated.
- Waiting room time will help determine intervention impact on wait time on the day of the appointment. To assess this, we will examine clinic- and facility-level data from the VHA Survey of Healthcare Experiences of Patients (SHEP), which includes several variables related to patient experience and satisfaction with wait time (e.g., “Wait time includes time spent in the waiting room and exam room. In the last 6 months, how often did you see this provider within 15 minutes of your appointment time?”). Our research team has been in communication with SHEP leadership and confirmed the feasibility of obtaining and analyzing these measures for our study sites. We also have experience with obtaining data use agreements for SHEP and linking data to individual Veterans. A sample size of approximately 4,000 subjects is available annually from SHEP data obtained from our study sites, many of who are likely to be included in the trial. We will conduct descriptive comparisons of Veterans in intervention and control arms.
- New mental health appointment wait time helps capture wait time for an important group: Veterans new to mental health. We will calculate this using another validated metric, defined as the length of time in days between the date the consult was created and the date the consult was completed⁸⁹.

These no-show, cancellation, and wait time metrics are consistent with ones used by our operational partners and VSSC. To construct these standardized measures, we will extract administrative data in CDW on appointment/encounter variables, including date, location, provider, stop code, and cancellation remarks. Wait time measures will be stratified based on new vs. established patients. “New patients” are those who have not completed another appointment in a given specialty and parent VA facility during the prior 24 months.

Baseline characteristics (Aims 2 and 3): To demonstrate balance among study arms, we will extract information from CDW on subject demographics (age, sex, race/ethnicity, service connection status, and rurality), diagnoses (proportion with common chronic conditions: depression, PTSD, diabetes, and hypertension), and appointment features (clinic type, new vs. follow-up, provider, and time between appointment creation and actual appointment). We will use protocols and code for data extraction previously established by Drs. [name] and [name] for these variables.

Qualitative assessment (Aim 4): The primary goals of our semi-structured interviews are to identify features of our interventions that act as facilitators or barriers to widespread implementation, and to suggest potential modifications or adaptations to the interventions that would promote larger-scale implementation, long-term maintenance, and adaptability to other reminder modalities. We will develop and pre-test interview guides for VHA staff and Veterans.

The VHA staff interview guide will be informed by selected constructs from domains (i.e. intervention characteristics, outer setting, and inner setting) in Consolidated Framework for Implementation Research (CFIR). CFIR is a widely used implementation framework, and bears relevance for our goals of conducting a formative evaluation prior to extensive implementation⁹⁰. Constructs selected will be those most relevant to the stage of pre-implementation, consistent with the scope of this proposal⁹¹. Interviews with VHA staff (n = 30, conducted remotely) will address issues such as the interventions’ relative advantage, adaptability, complexity, and design quality and packaging, as well as features across and within varying VA facilities and operational offices that might impact implementation. Potential barriers to implementation, such as unintended consequences of the intervention, impacts on clinical workflow, and existing clinic practices (e.g., overbooking), will bear special attention in interviews. Likewise, we will solicit suggestions on how to overcome such barriers. In order to promote potential adaptation and implementation of the intervention to text messaging-based appointment reminders, interviews will explicitly explore issues related to use of this newer modality of reminder delivery. Interviews with the Office of Connected Care, which oversees the “Annie” app that employs text messages, will be especially targeted to these

discussions. Interviews will last approximately 45-60 minutes, and be audio-recorded and transcribed.

The Veteran interview guide will be informed in part by the intervention characteristics domain within CFIR. Interviews with Veterans (n = 10, conducted in-person at VAPORHCS or remotely) will identify relative advantage of letter and postcard reminders, adaptability to other Veteran populations, and Veterans' support needs if the intervention were used implemented more broadly. We will also probe Veteran perspectives on barriers and facilitators to expanding the intervention to other non-postal modes of appointment reminder delivery. Specifically, we will probe adaptations to the intervention (e.g., timing, frequency, and length of reminders) that would make it more appropriate to deliver by phone (AudioCare), secure messaging (MyHealtheVet), and/or text messaging (Annie app, VEText).

J. Data Analysis:

Aims 2 and 3: We will first conduct univariate analyses to describe the “Table 1” baseline demographic, diagnostic, and appointment utilization characteristics of subjects and clinics in the usual care and intervention conditions. Then we will tabulate the total number of no-shows and total number of unique subjects with at least one no-show during the study period. For subjects with no-show(s), we will calculate the proportion with a single vs. multiple no-shows, and the mean and median number of no-shows. To analyze our primary outcome, no-show rate, we will use standard mixed effects correlated logistic regression since the outcome is binary at the individual-level. (We will use a similar approach to analyze intervention effects on our secondary outcomes, cancellation rates.) These will model the odds of no-shows as $\log[\text{odds}(p_{ij})] = b_i + \beta_0 + \beta_1 * \text{trt}(1)_{ij} + \beta_2 * \text{trt}(2)_{ij} + \beta_3 * \text{trt}(3)_{ij} + \beta_4 * \text{trt}(4)_{ij} + \text{location}_{ij}$, where p_{ij} is the no-show probability for provider i in location j , $\text{trt}(k)$ are indicators for the 4 interventions, and location_{ij} corresponds to the location for provider i . The random effect, b_i , is assumed to be normal with mean 0 and constant variance (σ^2_b) and will be used to account for repeated measures correlation for the individual subject outcomes for each provider; the model parameters, ($\beta_1, \beta_2, \beta_3, \beta_4$), represent log odds ratios of no-shows comparing the four intervention groups to the control group. They will be estimated using maximum likelihood estimation and will be used to test the hypotheses of Aim 1. This mixed model is a longitudinal model and can accommodate some forms of missing data, provided the missingness mechanism is non-informative. We can also estimate absolute risk differences between the interventions and usual care. No-show rates will also be presented in several ways: overall rate (i.e., for all study participants in each of the five study arms), stratified by specialty (mental health vs. primary care), stratified by patient type (new vs. follow-up), and over multiple follow-up periods (six and 12 months to determine duration and decay over time of any effect). We will also conduct exploratory subgroup analyses, which may identify particular patient populations where

effectiveness of interventions varies. For example, we will explore whether the effect of the interventions differ between men and women. To analyze our exploratory outcomes on appointment wait time, we will evaluate time-to-completed appointment using an extended multivariate Cox regression model to account for multiple appointments at the patient level and clustering at the provider level.

Aim 2 Hypotheses: To address Hypothesis 1 (Each intervention group will have a lower no-show rate, as compared with usual care) and Hypothesis 2 (Each intervention group will have a higher cancellation rate, as compared with usual care), we will conduct pairwise comparisons to test for differences between the interventions and usual care as $H_0: \beta_j=0$ for Interventions $j=1,2,3,4$.

Aim 3 Hypothesis (Effect size of nudges will vary by intervention arm such that some categories of nudges have a larger proportional effect than others): We will conduct pairwise comparisons of no-show and cancellation rates by testing the linear combinations between each of the four intervention arms (e.g., Intervention 1 and Intervention 2; $H_0: \beta_1=\beta_2$).

Aim 4: ATLAS.ti software will be used for data management. We will employ a “rapid assessment process,” which is useful for quickly developing understanding from an insider’s perspective and informing future implementation efforts^{81,92}. This multi-step process will be as follows: 1) create domain names for each interview question; 2) create and test a summary template; 3) summarize interview transcripts using the summary template, and 4) transfer summaries into a matrix (respondent x domain) data display⁹³. Our summary template will consist of domains and constructs from our interview guides (i.e., CFIR), and we will compose a templated summary for each interview. We will review these summaries on a regular basis (approximately every five interviews) to ensure interviews build iteratively on emergent findings.

